### **9.1.3 Vital Signs**

The following vital signs will be measured in accordance with the [Schedule of Events](#):

- Resting BP (systolic and diastolic)
- Resting HR
- Body temperature (°C or °F)

To avoid variability, the same method of obtaining body temperature should be used throughout the study.

#### **9.1.3.1 Blood Pressure Management**

Blood pressure and HR will be measured with the subject in a sitting position after 5 minutes of rest. The procedure for standardized measurement of BP is detailed in [Appendix 2](#).

If the BP measure is confirmed to be >130/80 mmHg (i.e., by the mean of the second and third repeats of 3 readings), the subject's BP will be managed per local practice. If the BP remains uncontrolled with the maximal doses of first and second-line antihypertensive therapies referenced in [Appendix 1](#), then the Investigator should contact the Medical Monitor to consider dose adjustment of the study treatment. See Section 7.9, [Increased Blood Pressure](#) for management of increased BP.

### **9.1.4 Standard 12-lead Electrocardiogram**

The electrocardiogram (ECG) will be a standard 12-lead tracing performed at the investigational site, assessed by a qualified physician at the investigational site, and retained as a source document. Any abnormalities will be recorded in the eCRF. Electrocardiograms will be recorded after the subject has been in a resting, supine position for at least 5 minutes. Abnormal ECG tracings can be reviewed by the Medical Monitor. Significant abnormalities, including findings that may prompt discontinuation of study treatment, must be discussed with the Medical Monitor.

Electrocardiograms will be measured at screening, Week 12, Week 24, and Week 52.

#### **9.1.4.1 Procedures to Manage a Treatment-Emergent Increase in QTc**

In the event that a subject has a QTcF value exceeding 500 msec, or an increase >60 msec from baseline, the Medical Monitor must be informed. The subject will be asked to return for an unscheduled visit within 24 hours and the ECG will be repeated (confirmed), in triplicate (i.e., three 10-second ECGs in rapid succession within 1 minute). If the repeat measurements confirm that the QTcF is >500 msec or >60 msec from baseline, the subject will be withdrawn from treatment with the study treatment and followed until the QTcF value either returns to baseline (or as appropriate) or until, in the judgment of the Investigator, further evaluation is not clinically indicated.

If study treatment is discontinued, the subject should continue in the study for all remaining scheduled study visits.

#### **9.1.5 Lupus Disease Activity Assessments**

The SELENA-SLEDAI assesses disease activity within the last 10 days. Twenty-four items are scored for 9 organ systems, and summed to a maximum of 105 points. A score of 6 is considered clinically significant. See [Appendix 6](#).

Assessments for SELENA-SLEDAI will be conducted at baseline, Week 24, and Week 52.

#### **9.1.6 Orelvo Pharmacokinetics**

Blood samples will be taken at Weeks 24 and 52. PK samples will be drawn prior to study treatment dosing (trough sample), and at 2 hours post-dose. These samples will be analyzed for Orelvo. Should a subject experience an SAE, require a dose modification or be withdrawn from treatment, a blood PK sample will be taken (with a trough sample preferred) for later determination of drug level. If a subject has discontinued from study drug treatment, further PK samples are not required.

### **9.2 Schedule of Assessments**

A detailed schedule of assessments (including all protocol-required assessments, visits, and visit windows) is located on the [Schedule of Events](#). No study related assessments will be performed (including changes to current medications to meet study eligibility) until the subject has provided signed and dated informed consent. Every effort will be made to keep the subject within the requested visit schedule. If a subject is seen outside of the visit window listed on the [Schedule of Events](#), the reason must be clearly documented in the source notes. The Investigator (or designee) should contact Aurinia for assistance with getting the subject's schedule back on track in order to avoid large variances in treatment exposure or to avoid delaying overall study timelines.

### **9.2.1 Screening Visit Procedures**

The screening visit (Visit 1) will take place within 30 days prior to Visit 2/baseline (Day 1). Screening will include provision of informed consent, physical examination including weight, and height, medical history (including SLE and LN history), vital signs measurements, 12-lead ECG, and review of prior and concomitant medications and entry criteria. Any AEs which occur after informed consent will be recorded. Urine samples will be collected for urinalysis and urine microscopy; first morning void urine samples (for determination of UPCR) will be collected on 2 days during the screening period and must be returned and the results evaluated prior to Visit 2. An average of the 2 screening UPCRs will be used as a marker of baseline urine protein excretion. Baseline proteinuria level is determined by a mean of 2 first morning void urine samples taken during the screening period. The lowest of pre-dose eGFR assessments will be used as the marker of baseline renal function. It is recommended that in the event that IV corticosteroids are administered during screening, the 2 first morning urine voids are to be collected prior to administration of the corticosteroids (see Section 7.2.2.2, [Corticosteroids](#)). In the case where this is not possible, then the marker of baseline urine protein excretion will be based upon the Visit 1 UPCR collection only. This must be discussed with the Medical Monitor prior to enrollment. Please note that the results of the 24-hour urine collection will have to be available prior to the Baseline Visit.

Blood samples will be drawn according to [Table 2](#).

If the subject is from an area where TB is endemic or whose history suggests an increased personal risk, e.g., from contact with people with TB or travel to areas with endemic TB, the subject will be carefully evaluated for latent or active TB.

Women of childbearing potential should have a negative serum pregnancy test result before randomization. Study treatment cannot be initiated by the physician until a report of a serum negative pregnancy test has been obtained.

If a subject has not met the requirements in Inclusion Criteria #4 due to not having kidney biopsy result within the required time frame, a kidney biopsy can be performed as per local procedures, after signing the study consent, provided the results can be obtained and reviewed prior to randomization.

### **9.2.2 Treatment Procedures**

Only subjects who satisfy all of the inclusion and exclusion criteria will be eligible for randomization and study treatment.

Subjects will be fasting for at least 8 hours on the day of randomization and all visit procedures must occur prior to the first dose of study treatment on Day 1. The MMF dose required per

protocol and IV methylprednisone (or oral corticosteroids) will also be administered at baseline before the first dose of Orelvo.

Subjects will complete all assessments per the [Schedule of Events](#) at Day 1, Day 2, and at Weeks 2, 4, 8, 12, 16, 20, 24, 30, 36, 42, and 48. IWRS will be accessed to assign study treatment to subjects at appropriate visits.

Adverse events and concomitant medication will be recorded prior to the conduct of other study assessments at each visit.

Assessments at visits during the treatment period include:

- SF-36 and LupusPRO HRQoL will be answered by the subject, as first study procedure, at Baseline, Week 12 and Week 24
- Physical examination including weight
- Vital signs
- ECG at Week 12 and Week 24
- Blood and urine sample collection for analysis at central laboratory
- First morning void urine sample collection, except before Day 1 and Day 2 Visits
- 24-hour urine collection at Week 24 (**IMPORTANT:** 24-hour urine collection will have to begin 2 days prior Week 24 visit in order not to coincide with the first morning void sampling due on the day of this visit)
- Pregnancy testing (serum: Week 24; urine: Day 1 and Weeks 2, 4, 8, 12, 16, 20, 30, 36, 42, and 48) and immunology
- AEs
- Concomitant medication
- SELENA-SLEDAI will be evaluated at Baseline and Week 24
- Dispense study treatment – including study treatment and background therapy
- Returned capsule count and drug accountability

- Information for the healthcare resource utilization assessment will be collected and recorded at Day 1 and Week 52

### **9.2.3 End of Study (or Early Discontinuation) Procedures**

On completion of treatment at Week 52 or earlier if subject is discontinued/withdrawn early, all assessments for Visit 15 (end of study/early termination) will be completed per the [Schedule of Events](#). See also Section 5.5, [Withdrawal of Subjects](#), for further information on withdrawal procedures and criteria.

The following assessments for the end of study visit will be performed:

- SF-36 and LupusPro HRQoL
- Abbreviated physical examination (including body weight)
- Vital signs
- Standard 12-lead ECG
- Blood sample collection for analysis at central laboratory
- Serum pregnancy testing
- First morning void
- 24-hour urine sample collection (**IMPORTANT**: 24-hour urine collection will have to begin 2 days prior to Week 52 visit in order not to coincide with the first morning void sampling due on the day of this visit)
- Concomitant medication
- AEs
- SELENA-SLEDAI
- Returned capsule count and drug accountability
- Confirmation of completion/discontinuation using IWRS
- Information for the healthcare resource utilization assessment will be collected and recorded

### **9.2.4 Follow-up Procedures**

All subjects who complete the study but do not participate in the continuation study or discontinue study treatment before Week 52 will be followed up 4 weeks ( $\pm 10$  days) after their last study treatment dose to collect any new AEs and concomitant medications. This visit (Visit 16) will be conducted as an in-clinic visit.

Assessments for the follow-up visit are as follows:

- Vital signs
- Blood sample collection for analysis at central laboratory (eGFR)
- First morning void urine sample collection
- Concomitant medication
- AEs
- Confirmation of completed follow-up visit using IWRS

### **9.2.5 Unscheduled Visit**

Unscheduled visits may be performed during the course of the study for safety reasons. An unscheduled visit is required 2 weeks after dose reduction at any time during the study. Only the data relevant to the purpose of the visit will be collected in the source documents and eCRF. An unscheduled visit is requested in the following cases:

- QTcF value exceeding 500 msec, or an increase  $>60$  msec from baseline, where the ECG will be repeated (confirmed) at an unscheduled visit
- Systolic BP is  $\geq 165$  mmHg or diastolic BP is  $\geq 105$  mmHg, or confirmed systolic BP  $>130$  mmHg or a diastolic BP  $>80$  mmHg
- Decrease in eGFR  $>30\%$  compared to baseline, or a confirmed decrease in eGFR  $>20-30\%$  compared to baseline
- Complete blood count must be performed locally at Weeks 1 and 3 in subjects not already taking MMF at the Screening Visit

## **9.3 Study Specific Assessment Procedures**

### **9.3.1 Health-related Quality of Life Assessments (HRQoL)**

#### **9.3.1.1 Short Form Health Survey (SF-36)**

The SF-36 HRQoL assessment is a 36-question subject HRQoL questionnaire and is presented in [Appendix 9](#).

#### **9.3.1.2 LupusPRO**

The LupusPRO (v1.7) is a 43-question subject HRQoL questionnaire specific for lupus and is presented in [Appendix 10](#).

### **9.3.2 Healthcare Resource Utilization Assessment**

The collection of information on healthcare resource utilization will be collected at the time points specified in the [Schedule of Events](#) (Day 1 and Weeks 24 and 52) and documented in the EDC system. This information will be collected via interview of the subject by the study staff and entered into the EDC system. General information collected may include:

- Type of insurance coverage
- Number of visits to ANY health care professionals (HCP), other than study doctor
- Types of HCP visited (specialists versus primary care)
- Time spent on visits
- Diagnostic tests performed
- Time spent by caregivers assisting patient with HCP visits (can ask general question if subject required a family member or other person to assist them to attend the visit)
- Prescriptions issued, filled
- Community services used

## **10. EVALUATION, RECORDING AND REPORTING OF AEs AND SAEs**

### **10.1 Definitions**

#### **10.1.1 Adverse Event**

Any untoward medical occurrence in a subject administered a pharmaceutical product and which does not necessarily have a causal relationship with this treatment is an AE. An AE can therefore be any unfavorable and unintended sign (including an abnormal laboratory finding), symptom, or disease temporally associated with the use of a medicinal (investigational) product, whether or not related to the medicinal (investigational) product.

#### **10.1.2 Adverse Drug Reaction**

In the pre-approval clinical experience with a new medical product or its new usages, particularly as the therapeutic dose(s) may not be established, all unintended responses to a medicinal product related to any dose should be considered adverse drug reactions (ADRs). The phrase “responses to a medicinal product” means that a causal relationship between a medicinal product and an AE is at least a reasonable possibility, i.e., the relationship cannot be ruled out.

#### **10.1.3 Serious Adverse Event**

An SAE (experience) or reaction is an untoward medical occurrence that at any dose meets 1 or more of the following criteria:

- Results in death (Note: death is an outcome, not an event)
- Is life-threatening (Note: the term “life-threatening” refers to an event in which the subject was at immediate risk of death at the time of the event; it does not refer to an event which could hypothetically have caused a death had it been more severe)
- Requires in-patient hospitalization or prolongation of existing hospitalization
- Results in persistent or significant disability/incapacity
- Results in a congenital anomaly/birth defect
- Is a medically important event or reaction

The definitions and reporting requirements of International Council for Harmonisation (ICH) Guidelines for Clinical Safety Data Management, Definitions, and Standards for Expedited Reporting, Topic E2 will be adhered to.

Medical and scientific judgment must be exercised in deciding whether expedited reporting is appropriate in other situations, such as important medical events that may not be immediately life-threatening or result in death or hospitalization but may jeopardize the subject or may require intervention to prevent one of the other outcomes listed in the definition above. These will also usually be considered serious.

Hospitalizations for elective or previously scheduled surgery for pre-existing conditions, which have not worsened after initiation of treatment, will not be classed as SAEs. Previously scheduled hospitalizations must be documented in the subject's source documents before the subject signed the informed consent form (ICF). A kidney biopsy performed as part of the study to verify eligibility will not be considered an SAE. Any complication experienced during a kidney biopsy procedure resulting in hospitalization or a prolongation of the hospitalization requires SAE reporting.

#### **10.1.4 Suspected Unexpected Serious Adverse Reaction**

Any ADR that is both serious and unexpected (per the IB) that, based on the opinion of the Investigator or Aurinia, is felt to have a reasonable suspected causal relationship to a medicinal product is a suspected unexpected serious adverse reaction.

### **10.2 Adverse Event Descriptors**

#### **10.2.1 Intensity/Severity Categorization**

The term "severe" is often used to describe the intensity (severity) of a specific event (as in mild, moderate, or severe myocardial infarction); however the event itself may be of relatively minor medical significance (such as severe headache). This is not the same as "serious," which is based on subject/event outcome or action criteria usually associated with events that pose a threat to a subject's life or functioning. Seriousness (not severity) serves as a guide for defining regulatory reporting obligations.

In general, the intensity of a particular AE to be recorded is the worst intensity experienced by the subject during the course of the event. The medical assessment of intensity will be determined by using the following definitions:

- Mild: The AE is easily tolerated and does not interfere with usual activity.
- Moderate: The AE interferes with daily activity, but the subject is still able to function.
- Severe: The AE is incapacitating and the subject is unable to work or complete usual activity.

### 10.2.2 Causal Relationship Categorization

An Investigator who is qualified in medicine must make the determination of relationship to the study treatment for each AE and SAE. The Investigator must decide whether, in his or her medical judgment, there is a reasonable possibility that the event may have been caused by the study treatment. If there is no valid reason for suggesting a relationship, then the AE/SAE must be classified as not related. Otherwise, if there is any valid reason, even if undetermined or untested, for suspecting a cause-and-effect relationship between the study treatment and the occurrence of the AE/SAE, then the AE/SAE will be considered related. For SAEs, the Investigator must provide a brief comment explaining the rationale of his/her assessment of causal relationship on the SAE reporting form.

The following additional guidance may be helpful:

Term	Relationship	Definition
Related	Yes	The temporal relationship of the clinical event to study drug administration indicates a causal relationship, and other drugs, therapeutic interventions or underlying conditions do not provide a sufficient explanation for the observed event.
Not related	No	The temporal relationship of the clinical event to study drug administration does not indicate a causal relationship, or other drugs, therapeutic interventions or underlying conditions provide a sufficient explanation for the observed event.

If the causal relationship between an AE/SAE and the study treatment is determined to be “related”, the event will be considered to be related to study treatment for the purposes of expedited regulatory reporting. In circumstances where the Investigator has not yet provided his/her assessment about the relationship, the event will be considered as “related” and qualify for expedited regulatory reporting.

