### 6.13.1 Adverse Events

A treatment emergent adverse event (TEAE) is defined as:

- Any AE that has an onset on or after the first dose of study drug up to last dose + 30 days. For subjects consenting to the AURORA 2 continuation study there will be an additional constraint to the TEAE definition: events must have an onset date prior to the first dose of AURORA 2 study drug.

A treatment-related TEAE is defined as a TEAE that is assessed by the Investigator or Sponsor as being related to study drug. If a TEAE has a missing relationship to study drug it is assumed to be related to the study drug for analysis purposes.

A disease-related TEAE is defined as a TEAE that is assessed by the Investigator or Sponsor as being related to the disease under study. If a TEAE has a missing relationship to the disease under study it is assumed to be related to the disease under study for analysis purposes.

Missing severity assessments will be summarised as severe.

The following tables will be presented for AEs:

- Summary table of overall incidence, the number of events, risk difference and 95% CI (voclosporin-placebo) including the following top line summaries:
  - Any AE
  - Any TEAE
  - Any Treatment-Related TEAE
  - Any Serious TEAE
  - Any Treatment-Related Serious TEAE
  - Any TEAE Leading to Voclosporin/Placebo Discontinuation
  - Any TEAE Leading to Death
  - Treatment-Related TEAE Leading to Death
  - Disease-Related TEAE
  - Disease-Related Serious TEAE

Detailed list of AE tables is given at the end of this SAP.

In counting the number of AEs reported, a continuous event (i.e., reported more than once and which did not cease), will be counted only once for a subject; a non-continuous AE reported several times by the same subject will be counted as multiple events.

Additional tables for serious TEAEs will be provided for each of the four regions: North America, Latin America, Europe/South Africa and Asia Pacific. Similar tables will also be provided for serious TEAEs occurring between day 1 and day 84 (Up to week 12), day 85 to day 168 (Week 12 to 24) and greater than day 168 (after week 24).

All AEs will be listed and a glossary of unique verbatim terms with coding information will be provided.

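### The causality guidance table in Protocol 10.2.2 is stricter than the mandatory text above it, and can only move adverse events from related to not related

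*Protocol*

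**What the plan says.** The text of Protocol 10.2.2 (Causal Relationship Categorization) sets a low threshold in mandatory terms. On one side: "If there is no valid reason for suggesting a relationship, then the AE/SAE must be classified as not related". On the other, the event is to be treated as related "if there is any valid reason, even if undetermined or untested, for suspecting a cause-and-effect relationship between the study treatment and the occurrence" of the event.

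A two-row table follows, introduced with the words "The following additional guidance may be helpful". It has a column for the term, one for the relationship and one headed Definition. *Related* requires timing that "indicates a causal relationship, and other drugs, therapeutic interventions or underlying conditions do not provide a sufficient explanation for the observed event". *Not related* applies when the timing "does not indicate a causal relationship, or other drugs, therapeutic interventions or underlying conditions provide a sufficient explanation for the observed event".

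Protocol 10.1.2 uses language close to the text. It explains a response to a medicinal product as one where "a causal relationship between a medicinal product and an AE is at least a reasonable possibility, i.e., the relationship cannot be ruled out". That sentence concerns adverse drug reactions and does not define the *Related* category, but it points the same way as the text.

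The call is used downstream. Protocol 10.2.2 ties it to expedited regulatory reporting. SAP 6.13.1 states: "A treatment-related TEAE is defined as a TEAE that is assessed by the Investigator or Sponsor as being related to study drug". SAP 6.11.1 lets an eGFR value disqualify a responder only if an eGFR-associated adverse event, related to treatment or to disease, is present on the date of the first such eGFR assessment.

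**The concern.** An investigator who follows the text and one who follows the table can classify the same event differently, and both can point to Protocol 10.2.2. The text asks only whether a valid reason for suspicion exists. The table adds two conditions: the timing must indicate causality, and no other drug, intervention or condition may sufficiently explain the event. Neither condition is in the text.

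Competing explanations will be a regular question in this trial. Every subject has active lupus nephritis and receives mycophenolate mofetil and corticosteroids alongside study treatment. At stake are the consistency of causality calls between sites, the counts in the treatment-related rows of the safety tables, the investigator's input to expedited reporting and, through one narrow route, the primary endpoint.

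**Working it through.** The plan gives no figure to reproduce, so the check is logical. Define three yes/no facts about an event:

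- V: there is a valid reason to suspect study treatment.
- T: the timing indicates a causal relationship.
- A: another drug, intervention or condition sufficiently explains the event.

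Text rule: related if V. Table rule: related if T and not A; otherwise not related. The table's two rows are exact complements, so it always gives an answer.

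Two assumptions are needed. First, T implies V, because timing that indicates causality is itself a valid reason for suspicion. This removes two of the 2 × 2 × 2 = 8 combinations and leaves 6. Second, A does not by itself cancel V: one cause can be sufficient while another remains reasonably suspected.

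| V | T | A | Text | Table | Agree? |
|---|---|---|---|---|---|
| no | no | no | not related | not related | yes |
| no | no | yes | not related | not related | yes |
| yes | no | no | related | not related | **no** |
| yes | no | yes | related | not related | **no** |
| yes | yes | no | related | related | yes |
| yes | yes | yes | related | not related | **no** |

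The tests disagree in 3 of 6 combinations. In all three the text gives related and the table gives not related; the reverse never occurs. Two of the three involve a sufficient alternative explanation. The third does not: the suspicion rests on something other than timing, and the table's timing condition alone turns the call. The 3 of 6 counts logical cases and is not an expected share of events.

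The disagreement then feeds three uses:

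- **Expedited reporting (Protocol 10.2.2).** A related call makes the event related for this purpose. An explicit not-related entry from the table removes the investigator's trigger.
- **Safety tables (SAP 6.13.1).** The rows for treatment-related TEAEs, treatment-related serious TEAEs and treatment-related TEAEs leading to death depend on the call.
- **Primary endpoint (SAP 6.11.1 and 6.11.2.3).** A fall attributed to study drug counts as treatment-related. A fall attributed to lupus counts as disease-related. A fall attributed to neither has no qualifying event, and SAP 6.11.2.3 then classes it as eGFR success even with eGFR below 60 and a confirmed decrease of more than 20%. Protocol 7.6.1.1 names NSAIDs, ACE inhibitors, ARBs and dehydration among possible contributors to eGFR falls. If study drug is validly suspected and one of these is judged sufficient, the text makes the event treatment-related and the fall disqualifies. Under the table the fall can be set aside.

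**The case against.** The strongest reply is that the table is optional and the text is not, so the text prevails. One can also read the two together: a truly sufficient alternative explanation is how an investigator concludes that no valid reason for suspicion remains. On that reading the two disagreements involving an alternative cause disappear. The reading is possible, but the protocol does not state it, and it leaves the timing-only disagreement in place. Nor does the introductory phrase settle the hierarchy for a site, because the table is laid out as the definition of the two terms.

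There are also real safeguards. All adverse events are recorded, and all SAEs are reported within 24 hours, whatever the presumed relationship (Protocol 10.3.1 and 10.3.2). Each SAE causality call needs a written rationale, and a pending assessment counts as related (Protocol 10.2.2). Suspected unexpected serious reactions rest on the opinion of the investigator or the sponsor (Protocol 10.1.4). SAP 6.13.1 accepts either party's assessment and treats a missing relationship as related. The overall TEAE, serious TEAE and exposure-adjusted tables do not use causality. These points limit the harm. They do not correct an explicit not-related entry, and the documents give no separate causality standard for the sponsor.

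A reader might infer more than the documents support:

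- That the table is the opposite of the text. It is not; the two agree wherever no valid suspicion exists.
- That any conceivable alternative cause is enough. The table requires a sufficient explanation, which is a higher bar, and having lupus or taking mycophenolate makes an alternative available without making it sufficient.
- That the Phase 2 infection, SAE and death figures in Protocol 1.2.4.2 show misclassification. They are all-cause figures from another study whose causality wording is not given, and Protocol 1.2.5 says that its DSMB also judged the deaths unrelated.
- That every eGFR fall with another explanation drops out of the primary endpoint. Falls attributed to lupus still count.

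**Conclusion.** The inconsistency is real and runs one way: read literally, the table is stricter than the mandatory text and can only move events from related to not related. It bears directly on the investigator's call for expedited reporting and on the treatment-related rows of SAP 6.13.1. It reaches the primary endpoint only for eGFR falls attributed to neither study drug nor lupus, and only if the sponsor has not independently called the event treatment- or disease-related.

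The number of events affected cannot be derived from the documents, and it is not established that sites will follow the table rather than the text. The direction rests on the assumption that timing indicative of causality is itself a valid reason for suspicion. The full set of three disagreements also assumes that a sufficient alternative explanation does not by itself remove a valid suspicion; without that assumption, one remains.

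**What to change.** Reword the table so that it restates the rule already in the text. *Related* should apply "if there is any valid reason, even if undetermined or untested, for suspecting a cause-and-effect relationship between the study treatment" and the event. *Not related* should apply only where there is no valid reason. No new standard is needed. Alternatively, delete the table and add one sentence saying that the text governs. Either way, align the eCRF completion guidance and remind sites.

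The cost is a wording change to the protocol and site guidance. The downside is that somewhat more events, and possibly more expedited reports, will be classed as related. The definition in SAP 6.13.1 can stay as it is, since it takes the investigator's or sponsor's call as given.
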